### 4.2 Baseline Analysis Set

The *Baseline Analysis Set* (BAS) consists of all patients of the APS and patients:

- where baseline signature has been taken (signed eCRF)
- with AF who are scheduled for Phased RFA
- that meet all remaining eligibility criteria
- provide any further documentation at baseline
- a phased RFA procedure was started - procedure form was fulfilled at least: date of the procedure, PVAC GOLD catheter used (opened), number of PV applications > 0
- patient did not exit the study prematurely for the reason: Patient were enrolled, but Phased RFA procedure was not started

According to the Appendix B, the BAS will be used for the interim and final analysis as well as for post-hoc analysis. The final analysis includes the additional objective (SAP chapter 8.2) and ancillary objectives (SAP chapter 8.3), where the BAS will be applied.

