### 4.3 Full Analysis Set

The *Full Analysis Set* (FAS) consists of all patients of the BAS and thereof patients with a valid 12MFU form of 12 months visit or 12 months telephone interview. The rules for valid 12MFU form are described in the chapter 7.2.3.

A documented 12MFU form includes at least:

- Date of the visit/FU and
- Vital status and
- Signed eCRF 12MFU visit or 12MFU by phone form

The FAS will be used to analyse the main objective (SAP chapter 8.1), additional objective (SAP chapter 8.2) and ancillary objectives (SAP chapter 8.3). The FAS will be analysed at the end of this study.

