## 4.4 Extended Full Analysis Set

The *Extended Full Analysis Set* (EFAS) consists of all patients of the FAS and thereof patients without documented AF re-ablation (each ablation technology i.e. additional GOLD-AF procedure) until the 12MFU (<351d after the first documented procedure). Also, only patients with a successful first documented procedure (by PVI confirmation) will be member of the EFAS. This population will be used to evaluate the effect of the first documented procedure, in a clearer way.

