### 7.2.4 Adverse Event data

Adverse event data (from AE form) will be listed, ordered and reported by seriousness and relatedness to the procedure. Further adverse event analysis are described in the additional objective of this study (SAP chapter 8 and 8.2). For Adverse event analysis only AEAC adjudicated (SUO form) events will be analysed.

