## 8.2 Statistical analyses for additional objective

### 8.2.1 Estimate Phased RFA procedure safety

Major procedure related complications include vascular complications secondary to venous access, cardiac tamponade, embolic stroke, esophageal injury, phrenic nerve injury, PV stenosis, reentrant tachycardia arrhythmias arising from ablations, mainly left Afl.

Adverse events (AE) including their relatedness to the respective procedure, are documented starting from the first documented procedure until the 12 month FU. For this analysis only adjudicated AE data (SUO form) and coded AE data (from free text fields) will be used. In addition, TIA/Stroke events will be taken from general FU forms to calculate procedure safety. Analysis will be performed at 30 days and at 12 months after procedure.

If no adverse event was documented within the 12 month FU period, the patient or the procedure is considered to be "free of AE". AEs are documented in the AE form, whereby distinctions in relatedness to which procedure (index phased RFA, repeated phased RFA or phased RFA re-ablation) will be made. Phased RFA procedure relatedness will also be taken from the AE form (Relatedness to Phased RFA procedure = related). The documented date of the AE will be used to set the point in time. For analysis purposes, phased RFA procedure safety will be calculated for first documented procedures (on procedure and patient level), separated for additional procedures (on procedure level) and for patients with additional procedures (on patient level).

Procedure safety will be calculated for procedures that have been carried out (number of RF applications per patient > 0) and disregarding procedure successfulness. This study objective will be calculated for the BAS and the FAS (Appendix B) for patients with signed eCRF.

Further analysis might be performed, e.g. procedure safety for using PVAC GOLD solely or not PVAC GOLD solely (using other catheter or using adjunctive devices).

**Table 7:** Procedure safety variables at AE form

AE due to definition	eCRF field: AE description	Related FID's annotated eCRF (V1.3, V1.4)
Vascular access complication	Vascular access complication 
 
• Hematoma or
 
• Arterio-venous fistula or
 
• Femoral artery pseudoaneurysm
 
	F31000010_6

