## 8.2.2 Methodology for analysing the procedure safety

The number of patients with reported device and procedure related events will be summarized as a binomial variables for each event and combined; number and percentage of events and patients with events (up to 12 month after first documented procedure). Additionally, Kaplan-Meier estimations (time-to-first-event analysis) will be used to summary the timing of the occurrence of safety events through 30 days and 12 months (351 days) after first documented procedure. Time from onset to resolution of events will also be presented. Further strata may be applied for analysis (e.g. reason for ablation: index, repeated, re-ablation, left Afl).

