## Appendix B: Analysis tables, Study objectives and Analysis sets

eCRF SEGMENTS	eCRF CHAPTERS/ANALYSIS TABLES	STUDY OBJECTIVES	ANALYSIS SETS FOR INTERIM ANALYSIS	ANALYSIS SETS FOR FINAL ANALYSIS
BASELINE	Enrolment		APS, BAS	APS, BAS, FAS, EFAS
	Indication/Admission		APS, BAS	APS, BAS, FAS, EFAS
	Demographics		BAS	BAS, FAS, EFAS
	History of CVD		BAS	BAS, FAS, EFAS
	History of AF		BAS	BAS, FAS, EFAS
	Symptoms		BAS	BAS, FAS, EFAS
	Concomitant Diseases		BAS	BAS, FAS, EFAS
	Diagnostics		BAS	BAS, FAS, EFAS
	Medications List		BAS	BAS, FAS, EFAS
	AFEQT		BAS	BAS, FAS, EFAS
	Anticoagulation (before/during first documented procedure)	ANCILLARY OBJECTIVE	BAS	BAS, FAS, EFAS
FIRST DOCUMENTED PROCEDURE	Administrative information		APS, BAS	APS, BAS, FAS, EFAS
	Procedure summary information	ANCILLARY OBJECTIVE	BAS	BAS, FAS, EFAS
	Consumables		BAS	BAS, FAS, EFAS
	PVI confirmation		BAS	BAS, FAS, EFAS
	Hospital discharge		APS, BAS	APS, BAS, FAS, EFAS
	Medication list at discharge		BAS	BAS, FAS, EFAS
ADDITIONAL PROCEDURE(S)	Administrative information		-	BAS, FAS, EFAS
	Procedure summary information	ANCILLARY OBJECTIVE	-	BAS, FAS, EFAS
	Consumables		-	BAS, FAS, EFAS
	PVI confirmation		-	BAS, FAS, EFAS
STUDY EXIT	Study exit		APS, BAS	APS, BAS, FAS, EFAS
AE	Administrative Information/Adverse Event	ADDITIONAL OBJECTIVE	-	BAS, FAS, EFAS
	Relatedness of the AE		-	BAS, FAS, EFAS
	Description of AE/AEAC		-	BAS, FAS, EFAS
GENERAL FU	Administrative Information		-	BAS, FAS, EFAS
	History of Arrhythmias since the last visit		-	BAS, FAS, EFAS

	Diagnostics		-	BAS, FAS, EFAS
	Symptoms		-	BAS, FAS, EFAS
	Hospitalizations		-	BAS, FAS, EFAS
	Medication List		-	BAS, FAS, EFAS
12MFU VISIT / 12MFU BY PHONE	Administrative Information		-	BAS, FAS, EFAS
	History of Arrhythmias since the last visit	MAIN OBJECTIVE	-	BAS, FAS, EFAS
	Diagnostics		-	BAS, FAS, EFAS
	Symptoms		-	BAS, FAS, EFAS
	Hospitalizations		-	BAS, FAS, EFAS
	Medication List		-	BAS, FAS, EFAS
	AFEQT	ANCILLARY OBJECTIVE	-	BAS, FAS, EFAS

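### Patients with vascular access who never receive an RF application enter no specified safety rate or Kaplan-Meier estimate, although the protocol retains them so that their related adverse events are collected

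*SAP*

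**What the plan says.** **SAP, analysis sets.** The BAS (4.2) treats a procedure as started only if the form holds at least: "date of the procedure, PVAC GOLD catheter used (opened), number of PV applications > 0". The Full Analysis Set (FAS, 4.3) takes BAS members and "thereof patients with a valid 12MFU form of 12 months visit or 12 months telephone interview". The Extended Full Analysis Set (EFAS, 4.4) "consists of all patients of the FAS and thereof patients without documented AF re-ablation".

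**SAP, safety analysis.** Section 8.2.1 sets the condition: "Procedure safety will be calculated for procedures that have been carried out (number of RF applications per patient > 0) and disregarding procedure successfulness". It then names the sets: "This study objective will be calculated for the BAS and the FAS (Appendix B) for patients with signed eCRF". Section 8.2.2 plans counts and percentages, and adds Kaplan-Meier estimates that "will be used to summary the timing of the occurrence of safety events through 30 days and 12 months". In Appendix B the row "Administrative Information/Adverse Event" and the two AE rows below it are assigned to BAS, FAS and EFAS at the final analysis. The All-Documented Patient Set (APS) is not listed there. Section 7.2.4 plans a listing without naming a set: "Adverse event data (from AE form) will be listed, ordered and reported by seriousness and relatedness to the procedure".

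**Protocol.**
- Section 7.2 (Study Exit) asks sites to keep patients with vascular access but no ablation energy enrolled for 30 days, so that procedure- or device-related AEs are assessed and collected.
- Section 7.2 (Procedure visit) says information from all Phased RFA attempts will be used in the analysis.
- Section 4.1 includes all enrolled patients in the analysis, and SAP 6.1 repeats this.
- Section 4.4.2 defines the safety endpoint with no RF condition.
- Section 4.4 allows additional selection criteria in specific analyses. It also says that changes of method, with their justification, will be described in the SAP.

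**The concern.** The RF condition is not neutral with respect to the outcome. The SAP's list of major complications in 8.2.1 includes vascular access complications and cardiac tamponade. Either can occur before the first application, and either can be the reason the procedure was stopped without energy. Where that happens, the complication itself removes the patient from the analysis meant to count it.

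The reported rate would then describe procedures that reached ablation, not all procedures in which access was obtained for Phased RFA. The second is the natural denominator for an objective about procedure safety, and the retention rule in protocol 7.2 appears to serve it. The SAP openly flags other departures from the protocol, namely the recurrence definition (8.1.1) and the follow-up windows (7.2.3). It neither flags nor justifies this one.

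**Working it through.** **Step 1: who is counted.** Applying SAP 4.2-4.4, 8.2.1 and Appendix B to four kinds of patient (other BAS conditions met):

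| Patient | In BAS? | Related complication in a specified rate or Kaplan-Meier estimate? |
|---|---|---|
| RF delivered, complication afterwards | Yes | Yes |
| Complication after access but before the first application, RF then delivered | Yes | Yes |
| Access obtained, RF never delivered | No, hence not in FAS or EFAS | No |
| Zero-RF index attempt, later repeat with RF | Possibly | Unclear: 8.2.1 counts applications per patient, so the index complication may or may not count |

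The third row is the finding. Two separate rules produce it, so deleting the condition in 8.2.1 alone would not cure it: the BAS carries an equivalent one. The peri-procedural TIA/stroke analysis under SAP 8.3 also runs on BAS and FAS.

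**Step 2: where else these patients could appear.** SAP 6.1 tabulates reasons for exclusion from the BAS. Appendix B puts study exit on the APS. The 7.2.4 listing might include single events. None of these gives a safety rate.

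**Step 3: size.** The documents give no count of zero-RF procedures and no safety figure to reproduce, so this is illustration only.

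- r = complication rate in patients with RF > 0. The two rates cited in protocol 4.4.2, 2.0% and 3.9%, are used as stand-ins.
- f = share of access procedures with no RF. Assumed 0.5% to 2%.
- c = complication rate in that share. Assumed 10% to 50%.
- Number of patients with access: 1000, assumed equal to planned enrolment.

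Rate in all access patients = (1 - f) x r + f x c. Shift = f x (c - r), which is zero if c = r. Patients with a complication left out per 1000 = 1000 x f x c.

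| f | c | Left out per 1000 | r = 2.0% becomes | r = 3.9% becomes |
|---|---|---|---|---|
| 0.5% | 10% | 0.5 | 2.04% (+0.04) | 3.93% (+0.03) |
| 1% | 30% | 3 | 2.28% (+0.28) | 4.16% (+0.26) |
| 2% | 50% | 10 | 2.96% (+0.96) | 4.82% (+0.92) |

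Middle case written out: 0.99 x 2.0% + 0.01 x 30% = 2.28%. Per 1000 patients, one missed patient is 1/20 = 5.0% of the complications expected at 2.0%, or 1/39 = 2.6% of those expected at 3.9%.

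**Step 4: against sampling error.** 95% half-width at n = 1000:
- r = 2.0%: 1.96 x sqrt(0.02 x 0.98 / 1000) = 0.87 points, or 0.95 with the protocol's design effect of 1.2.
- r = 3.9%: 1.96 x sqrt(0.039 x 0.961 / 1000) = 1.20 points, or 1.31 with the design effect.

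Over f = 0.5, 1, 2%, c = 10, 30, 50% and both values of r (18 combinations), only f = 2%, c = 50%, r = 2.0% exceeds the half-width. With the design effect it does so by 0.01 points.

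**The case against.** **Patients who received RF are a legitimate population, and protocol 4.4 allows extra selection criteria.** Both statements are true. RF > 0 suits a question about device performance and should be kept for that. But the same section of the protocol expects a change of method to be justified in the SAP. SAP 8 moves such justification to the study report, and no reason for the RF condition appears.

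**The exclusion is not hidden.** This stands in part. The exclusion overview, the APS study-exit table and the AE listing may reveal the excluded patients, a death or a single event. They do not put these events over a denominator.

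**The effect is probably small, and the registry is descriptive.** This largely stands. The values of f and c are assumptions, and nearly all combinations fall within sampling error. Still, if c exceeds r the error always runs in the favourable direction, and more patients do not reduce it.

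**A stronger reading does not hold.** A reader might infer that every complication before the first RF application is lost. The documents do not support that. Exclusion depends on RF never being delivered, not on when the event occurred, so an early complication in a patient who goes on to receive RF is counted in the BAS. Nor can one say that every zero-RF attempt is lost, given the per-patient wording when a repeat procedure follows.

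**Conclusion.** The point holds for patients with vascular access obtained for an intended Phased RFA who never receive an RF application. Their procedure- or device-related complications enter no specified safety rate or Kaplan-Meier estimate, although the protocol provides for collecting them. This follows from the text of the set definitions and needs no assumption.

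The size is not known. Understatement requires c > r, which is plausible when complications cause the stop but is not shown in the documents. Under the assumed ranges the shift is between 0.03 and 0.96 points. The documents therefore do not support a claim that the reported rate will be materially wrong. The case for change is that the denominator can depend on the outcome, departs from the protocol without a stated reason and is cheap to correct. It should be fixed.

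**What to change.** 1. Add to SAP 4 a safety set: all patients in whom vascular access was obtained for an intended Phased RFA, regardless of RF applications or a 12-month form. Identify it from the first vessel access time used in SAP 7.4.1 (Procedure Timing). Where that field is empty, use the procedure, AE or exit form.
2. Use this set for the rates and Kaplan-Meier estimates in SAP 8.2.1-8.2.2 and for the AE rows of Appendix B. State in 7.2.4 that the AE listing covers it.
3. Set day 0 at the first procedure with access, so that events after a zero-RF index attempt count even if a repeat follows. Censor at last study contact.
4. Do not censor at a switch to another ablation technology, because access complications recognised after the switch would be lost. Count these patients to last contact or study exit, use the adjudicated relatedness to Phased RFA, and also show them separately.
5. Make the 30-day rate the main comparison. Take the 12-month figure from Kaplan-Meier, because a crude percentage would treat patients who leave early as event-free.
6. Reconcile the follow-up passages. The synopsis (Individual FU duration), protocol 3.4 and 7.2 (Procedure visit) keep patients with an unsuccessful index procedure in the registry, the first two until the end of follow-up. Protocol 7.2 (Study Exit) speaks of 30 days for patients without energy, and its next sentence breaks off.
7. Keep RF > 0 (BAS) as a secondary analysis.

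**Cost.** Changes to SAP wording, clarification of the protocol's follow-up passages and a little more analysis work. The protocol already provides for collecting these AEs. The documents do not show whether the access time is completed for aborted cases, hence the fallback in item 1. The reported complication rate may be slightly higher.

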## 8.2.2 Methodology for analysing the procedure safety

The number of patients with reported device and procedure related events will be summarized as a binomial variables for each event and combined; number and percentage of events and patients with events (up to 12 month after first documented procedure). Additionally, Kaplan-Meier estimations (time-to-first-event analysis) will be used to summary the timing of the occurrence of safety events through 30 days and 12 months (351 days) after first documented procedure. Time from onset to resolution of events will also be presented. Further strata may be applied for analysis (e.g. reason for ablation: index, repeated, re-ablation, left Afl).

## 8.3 Statistical analyses for ancillary objectives

According to Appendix B, these analyses will be performed for the Baseline Analysis Set and Full Analysis Set. If not described otherwise, ancillary objectives will be analysed using methods of descriptive statistics (SAP chapter 8).

### 8.3.1 Characterize the acute procedural success rate

Success rates will be calculated for all documented procedures combined (patient level). Also, procedure success rates will be provided for first documented procedures, additional procedures, regular cases and training cases, separately. Success rates will also be shown per vein.

Success will be calculated for procedures that have been attempted (number of RF applications per patient > 0). Success rates will be provided for PVAC GOLD solely procedures (ancillary objective) and additionally for not PVAC GOLD solely procedures (using other catheter and/or using adjunctive devices).

If RF applications per patient, consumables (Phased RFA catheters used), successfulness and PV confirmation (exit or entrance block) was not verified for the procedure, the data will not be used for analysis. Consumables and procedure success will be taken from the procedure form. Relatedness of Phased RFA will be taken from AE form.

The procedure is considered successful if:

- Procedure attempt was not declined due to technical issues related to Phased RFA system and
- Only PVAC catheter(s) used to achieve PVI and
- All accessible PVs were isolated (entrance and/or exit block confirmation per vein)

This combined endpoint (variables linked via “and operation”) is applicable, if all conditions are available and complied.

Because of different procedure forms (eCRF V1.3 and eCRF V1.4), PVI achievement by PVAC GOLD only is assumed for patients documented by eCRF V1.3 as follows:

- [F21000010] Phased RFA catheter used: only PVAC GOLD is ticked, and
- [F22000010] to [F22000060] PVI confirmation: exit block and/or entrance block are ticked, and
- [F20001000] Number of RF applications per patient > 0

Unsuccessfulness per vein is considered, if the vein is not isolated or not verified. Percentages for success will be shown per vein for patients treated with PVAC GOLD solely. Precondition is that the number of RF applications per patient is greater than zero.

PVI achievement by PVAC GOLD only is defined for patients documented by eCRF V1.4 as follows:

- [F21000010] Phased RFA catheter used: only PVAC GOLD is ticked, and
- [F22000062] Where all PVs isolated at the end of the procedure = yes, and
- [F22000066] Where all PVs isolated by using PVAC only = yes, and
- [F21000010] Number of RF applications per patient > 0

Unsuccessfulness per vein is considered, if the vein is not isolated or not verified. Percentages for success will be shown per vein for patients treated with PVAC GOLD, all PVs were isolated at the end of the procedure = no and all PVs isolated by using PVAC only = no.

**Table 9:** Procedure success variables from Procedure and AE form

Objective section	Definition (used variables)	Related FID's annotated eCRF (V1.3, V1.4)
Procedure attempt was not declined due to technical issues related to Phased RFA system	Procedure form: Date of procedure Phased RFA procedure successful?  No – Due to AE AE form: Date of AE Was the event related to technical issues?* Related/Possibly related	F20000010 F22000180 F22000190  F30000010 F30000070
Only PVAC catheter(s) used to achieve PVI	Procedure form: Phased RFA catheters used PVAC GOLD (solely) Number of RF applications per patient > 0  Were all PVs isolated at the end of the procedure Were all PVs isolated by using only PVAC	eCRF V1.3/V1.4 F21000010  F20001000 eCRF V1.4 only F22000062  F22000066

All accessible PVs were isolated (entrance and/or exit block confirmation per vein)	Were all accessible PVs isolated at the end of the procedure entrance block and/or exit block Exit block and/or Entrance block	eCRFV1.3/V1.4 F22000010 F22000020 F22000030 F22000040 F22000050 F22000060
---	--	---

\* Precondition: If the documented AE is related to technical issues with Phased RFA system components, the date of the latest procedure must be  $\leq$  date of the AE. For patients with more  $> 1$  procedure, the latest procedure will be the related procedure.

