In previous studies with Phased RFA an average acute procedural success of 98.2% (93-100%) was reported in patients with paroxysmal AF (23 studies). This is similar to the average acute procedural success reported for patients (6 studies) with persistent AF of 96.3%. In the case of index procedural failure, the authors linked the failure to the patient anatomy or characteristics and not to the Phased RFA system.

Endpoint definition:

- Procedure attempt was not declined due to technical issues related to Phased RFA system
- Only PVAC catheter(s) used to achieve PVI
AND
- All accessible PVs were isolated (entrance and/or exit block confirmation per vein)

If exit or entrance block was not verified during the procedure the data will not be used for this analysis.

Analysis Method: Acute procedural success rate will be reported as frequency and percentage at both the patients and vein level. Acute procedural success rate by patients will be calculated as number of patients with acute procedural success divided by number of patients with an attempted Phased RFA procedure. Acute procedural success rate by vein will be calculated as number of veins with electrical isolation verified divided by number of veins attempted with Phased RFA. 95% confidence intervals will be calculated using Fisher's exact method.

Limitation: Even though PVAC GOLD catheter has been designed anatomically, steerability can be influenced by the sheath used with the catheter. With fixed curve sheath might become challenging to reach all PVs, in particular right inferior PV due to technical issues. Due to this additional use of 3D system and irrigated catheters might be utilized by the medical centers where steerable sheath is not available.

Assess Phased RFA efficiency

Rational: The multi electrode catheter technology delivers continuous lesions and shortens procedure times. The ability to map and ablate with the same electrode simplifies and shortens the procedure.

Procedure duration is impacted by the maneuverability of the catheter. The new catheter design of the PVAC GOLD array allows enhanced tissue contact due to the 20° forward tilt.

Hospital resource allocation is another indicator of procedural efficiency, reflected by the procedure duration ("from skin to skin"), laboratory occupancy ("from door to door"), fluoroscopy time as well as number of used catheters and adjunctive devices (mapping and navigation) used.

Endpoint definition:

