11.3.1 Device Deficiencies

Device deficiency information is not to be collected throughout the study, though can be adjudicated by the aforementioned AEAC.

12 Legal Requirements

This registry fulfils the requirements of the Directive 2001/83 EC, title IX and Volume 9A of The Rules Governing Medicinal Products in the EC, the Declaration of Helsinki 2013 and later versions throughout the study (30) and will be conducted in accordance with the respective SOPs of Medtronic and CRO (IHF). The applicable SOPs for the study will be determined prior to study initiation and updated throughout the study.

Documented approval of the CIP is required from the following groups prior to any study procedures at a study site:

- Medtronic
- CRO (IHF) approvers
- An independent EC (if required)
- Principal Investigator (PI) (where required by local law)
- Geography-specific regulatory authorities (if regulatory approval is required)

Similarly, approval of subsequent revisions to the CIP is required based on the revised contents at each study site from the above mentioned groups prior to implementation of the revised CIP at that site.

13 Steering Committee

The Steering Committee (SC) will be an advisory body to the GOLD AF registry. SC members are responsible for collaboration and guidance on study goals, design and execution and other activities based on expertise and as agreed upon consultancy agreement with the sponsor. Contact information will be provided under the separate cover. This information can be updated throughout the course of the study. The updated list will be maintained at Medtronic and will be available upon request.

14 Final Report and Publications

A final report will be prepared following the last patient has exited the study and the database has been locked.

Medtronic may form the GOLD AF Publication Committee from Steering committee members, study Principal Investigators and Co-Investigators. Medtronic study personnel may serve as members of the committee. This committee will manage study publications with the goal of publishing conclusions and results from the data.

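### Acute success leaves out Phased RFA attempts stopped by a system fault before any energy, and reads the technical criterion only through an adverse event

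*SAP*

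**What the plan says.** - **Denominator.** SAP 8.3.1: "Success will be calculated for procedures that have been attempted (number of RF applications per patient > 0". SAP 8.3.1.1 then divides patients with acute success by patients with an attempted procedure.
- **Analysis set.** Under SAP 8.3, "these analyses will be performed for the Baseline Analysis Set and Full Analysis Set". SAP 4.2 admits a patient to the BAS only if the procedure form gives at least "date of the procedure, PVAC GOLD catheter used (opened), number of PV applications > 0". The FAS is a subset of the BAS.
- **Success.** Both documents require three things together: (1) "Procedure attempt was not declined due to technical issues related to Phased RFA system"; (2) only PVAC catheters used to achieve PVI; (3) every accessible vein isolated, with entrance or exit block confirmed.
- **Source for criterion 1.** SAP Table 9 uses the procedure-form answer that the procedure was unsuccessful because of an AE, then the AE-form item "Was the event related to technical issues". The text adds: "Relatedness of Phased RFA will be taken from AE form". No other source is listed for this criterion.
- **Unverified block.** Protocol 4.4.3 and SAP 8.3.1 leave such procedures out of the analysis. The SAP's vein-level rule instead treats an unverified vein as unsuccessful.
- **Zero-energy and technical stops elsewhere.** Protocol 7.2 says that data on all Phased RFA attempts will be analysed. It also foresees patients with vascular access who receive no ablation energy and keeps them enrolled for 30 days. Protocol Appendix 1 lists termination for technical issues under unsuccessful procedures. Protocol 11.3.1: "Device deficiency information is not to be collected throughout the study".

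**The concern.** The first criterion is the part of the endpoint that speaks to the reliability of the system. Its clearest failure is an attempt given up for a system fault before anything is ablated. The SAP removes that case before the criterion is applied, through the meaning it gives to an attempt and again through the BAS.

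For procedures that remain, criterion 1 depends on an AE. Protocol Table 11-2 defines an AE as an untoward medical occurrence, so a generator or catheter fault that harms nobody need not produce one. Device deficiencies are not collected, which closes the other obvious route.

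At stake is whether the published acute success rate describes all attempts, as the protocol's denominator suggests, or only those in which the system delivered energy.

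**Working it through.** The plan computes no figure on this point, so there is nothing to reproduce. The check has two parts.

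**1. How each kind of technical stop is classified at patient level.** The filters (application count, verified data) act first; the three criteria are then joined by a logical AND.

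| Situation | Result under the SAP |
|---|---|
| a. No energy delivered, with or without an AE | Outside the denominator and outside the BAS; never a failure |
| b. Energy delivered, no AE, an accessible vein recorded as not isolated | Criterion 1 not triggered; criterion 3 fails: failure |
| c. Energy delivered, no AE, PVI completed with a non-PVAC catheter | Criterion 2 fails: failure where it is analysed (the SAP reports PVAC GOLD solely and not-solely procedures separately) |
| d. Energy delivered, no AE, block not verified | Dropped; not a failure, although the vein-level rule would call the vein unsuccessful |
| e. Fault without an AE, all veins isolated with PVAC only | Success |

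Technical aborts escape in rows a and d. Rows b and c are caught without any AE. Row e is a completed procedure, not an abort.

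**2. Size of row a.** Let N be all attempts, k the zero-energy technical aborts and x the successes.

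- SAP rate = x / (N − k)
- Rate with the aborts counted as failures = x / N

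Inputs: N = 1000 for illustration, matching the planned enrolment (Protocol 4.3). The success rate among procedures with energy is set at 98.2%, the paroxysmal AF background figure in Protocol 4.4.3. The abort share k/N is an assumption, because the documents give none. x is (N − k) × 0.982, rounded.

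| Assumed k/N | x | SAP rate | Rate over all attempts |
|---|---|---|---|
| 0.5% | 977 | 977/995 = 98.2% | 977/1000 = 97.7% |
| 1% | 972 | 972/990 = 98.2% | 972/1000 = 97.2% |
| 2% | 962 | 962/980 = 98.2% | 962/1000 = 96.2% |

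At 2%, with exact (Clopper-Pearson) 95% intervals, the SAP rate is 98.16% (97.11 to 98.91) and the all-attempts rate is 96.20% (94.82 to 97.30). The second estimate lies below the lower limit of the first. Starting from the protocol's 96.3% for persistent AF, 2% aborts give 944/980 = 96.33% against 944/1000 = 94.40%.

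Because x/(N − k) is never below x/N, leaving these aborts out cannot lower the rate.

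**The case against.** A reader might infer that a technical abort without an AE can never count as a failure, or that criterion 1 is met almost by definition and takes the endpoint with it. The documents do not support that. Criteria 2 and 3 come from the procedure form and need no AE, so rows b and c fail on their own. The gap is confined to zero-energy stops and to post-energy stops with unverified block.

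Other points on the plan's side:

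- **The protocol does not define an attempt, and SAP 8.3.1.1 repeats its denominator.** True: the SAP narrows the term rather than openly replacing the ratio. But the protocol attaches no energy condition, foresees zero-energy cases and says all attempts will be used.
- **The protocol has its own exclusion for unverified block, which would usually remove a zero-energy abort anyway.** This stands. It sits badly with the first criterion, and redefining an attempt would not be enough by itself.
- **Not every zero-energy stop is a system fault.** Also right. Criterion 1 concerns the Phased RFA system; stops for access or patient condition are a different matter and should not be folded in.
- **Exclusions will be visible.** SAP 6.1 plans a table of reasons for exclusion from the BAS. That is useful disclosure but leaves the reported rate unchanged.
- **The endpoint is ancillary and descriptive, with no hypothesis test.** True, and it limits the consequence.

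**Conclusion.** The point holds in a limited form. A Phased RFA attempt abandoned for a system technical issue before any energy is removed from acute success instead of counting against it. After energy, a technical abort without an AE is a failure only if it also fails the PVAC-only or isolation criterion on verified data. If block is unverified, it is dropped at patient level, in conflict with the vein-level rule.

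The direction of the zero-energy exclusion is certain: it can only flatter the rate. The size is not known. If zero-energy technical aborts are 0.5% to 2% of attempts and 98.2% of the rest succeed, the rate over all attempts is 97.7% to 96.2%, an overstatement of about 0.5 to 2.0 percentage points. Both inputs are illustrative: the abort share is assumed, and the 98.2% is a literature average for paroxysmal AF applied to a mixed registry. A gap of that order would matter for a rate this close to 100%, and the correction is cheap.

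**What to change.** For the acute success endpoint only:

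1. Define an attempt independently of energy: vascular access obtained, or a Phased RFA catheter opened, with intent to perform Phased RFA.
2. Exempt the endpoint from the application-count condition in the BAS. Changing SAP 8.3.1 alone would not bring these procedures back.
3. Do not apply the unverified-block exclusion to procedures stopped for Phased RFA system technical issues. Count them as not successful.
4. Identify those stops from the procedure form's reason for failure, where such a field exists, as well as from the AE form. The annotated eCRF is not among the documents available here, so the field must be confirmed.
5. Report zero-energy stops for access or patient-condition reasons separately, by number and reason.
6. State whether an unverified vein is excluded or unsuccessful, so that the patient-level and vein-level rules can be read together.

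The cost is a few sentences in SAP 4.2, 8.3.1 and Table 9, and a slightly lower rate. Point 3 departs from a sentence in Protocol 4.4.3. Protocol 4.4 requires an amendment only when a change alters the main and additional objectives; otherwise the change and its justification go in the SAP.
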